Newborn infants diagnosed with neonatal encephalopathy undergoing cooling therapy for neonatal encephalopathy irrespective of gender or race are eligible for this study. We aim to recruit patients both in English and Spanish.

All four of the following criteria must be met to qualify for the cooling protocol

1. Age: less than 1 day old
2. Gestational age > 35wks
3. Evidence of birth depression, either
 - a. 10 minute Apgar score less than 5
 - b. Need for cardiopulmonary resuscitation at 10 minutes of age
 - c. Blood pH < 7.0 within the first 1-hour of life
 - d. Base excess lower than -12 (i.e. base deficit more than 12) within the first hour of life
4. Evidence of encephalopathy based on clinical (neurological examination) or on aEEG/cEEG assessment.

Exclusion Criteria:

1. Major congenital or genetic abnormalities
2. Infants more than one day old
3. Known allergy/sensitivity or any hypersensitivity to components of study drug
4. Maternal illicit drug or alcohol use during pregnancy
5. If the baby had a proven (i.e. electrically confirmed seizure) prior to enrollment

5) Study Timelines

We expect to complete this study within 2 years. We have 13 patients already enrolled and our goal is 42 total (study arm n=21 and control arm n=21). We have chosen a sample size of 42 as this sample size will have an 80% chance of detecting a reduction of seizure rate by 2/3 with a p-value of 0.05.

At our institution alone we have ample experience in whole body cooling having cooled 31 patients in 2015, 28 patients in 2016, and most recently 26 patients in 2017. Patients will be asked to come for a one hour follow up outpatient clinic (MIND Institute) visit at the at 9, 18, and 27 months of age (all infants who receive cooling are asked to complete this follow-up, including those not in this study).

6) Study Endpoints

Our primary study endpoint remains to conclude if our current modality of whole-body cooling coupled with topiramate results in seizures or no seizures.

As well to determine the effect of adjuvant topiramate treatment on the outcome of newborns with perinatal depression (including neonatal encephalopathy) who are already receiving the therapeutic whole body cooling.

7) Informed Consent

One or both parents of the eligible infants are approached either

- (1) In person in the NICU at UCDMC by one of the investigators
- (2) By our Transport Nursing staff or Neonatal Fellow (if they are still at the outside referral center)

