Infants assigned to the topiramate group will receive 5mg/kg of topiramate daily enterally for a total of 5 doses. This is the minimum therapeutic dose of topiramate for infants. The first dose will be administered on the day of enrollment and will continue through and after rewarming. The duration of drug administration was chosen to encompass the cooling period as well as a brief period after rewarming is complete as this is a period where some infants develop seizures and display more signs of neurological damage. The control group will receive a placebo instead of topiramate. Pharmacy will prepare and send to NICU the placebo or study drug solutions in a way to be similar in appearance and volume. Initiation of cooling will not be delayed, but families will be approached for consent as soon as possible after cooling has started.

The cooling protocol includes a range of laboratory evaluations which will be carried out irrespective of whether the patient is enrolled in the study. These include: complete blood count, PTT/INR, DIC panel, complete metabolic panel, ammonia, lactate, troponin-I, CK panel, blood gas, and urinalysis at the initiation of cooling and then every 24h until rewarming is complete (unless the Attending Neonatologist decides that more frequent or less reassessments are needed clinically). Blood gases, blood glucose and ionized calcium levels are measured at the initiation of cooling and then every 6h until rewarming is complete. Once labs have normalized per the discretion of the covering Attending some of these labs may be discontinued. These lab values will provide important data of the severity of each infant's hypoxic-ischemic insult and for patient safety monitoring including information on liver function, kidney function, ammonia toxicity, metabolic status, and acidosis. Enrollment in the study will not change the frequency of these assessments.

A single channel EEG recording (an amplitude EEG, aEEG) or continuous video EEG is recorded continuously on all patients until rewarming is complete. This method measures the degree of encephalopathy and detects seizures.

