Meier analysis. The effect of treatment on S100 β levels in the urine or UHCL1 in the blood and on other markers of tissue injury will be compared using ANOVA (for outcomes measured once) and by repeated measures ANOVA for those measured on more than one occasion, at predetermined times.

Effect of treatment assignment of development assessments will be assessed individually at the 9m, 18m and 27m examinations.

All tests will be considered significant at $p<0.05$. Where necessary, Tukey-Kramer's test will be used to account for multiple comparisons

Data Specimen/Management

Data specimens will be stored in the NICU and numerically coded, only those who are involved with this study will have access to the specimens. The specimens will only be stored for the duration of the study and thereafter discarded.

10) Data and/or Specimen Banking

There is no plan for specimen or tissue banking in the future.

11) Provisions to Monitor the Data to Ensure the Safety of Subjects

To monitor the safety of each newborn we will track the following variables closely during the intervention: blood gases, blood pressure (hypotensive episodes and required interventions), evidence of seizure activity, and serum topiramate levels. This study is only applicable to newborns with neonatal encephalopathy admitted to the NICU at UC Davis for cooling therapy. Neonatal encephalopathy is a life threatening disease with 30% chance of death and 64% chance of seizures during the neonatal period. These patients receive 24 hours daily continuous extremely close physiological and biochemical monitoring based on their underlying disease state.

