A Data Safety Monitoring Committee (DSMC) will be utilized for this study. A report will be sent to the chairman of the DSMC every 6 months. He will share this with the other members and meetings will be carried out either by e-mail or face-to-face as the chairman sees fit. The DSMC will remain blinded to study assignation, but will receive summary data for every patient including which agent the patient received (designated as "Study drug A" or "Study drug B"), their short term outcome (incidence of seizures and survival to hospital discharge) and the number of doses of sodium bicarbonate and bronchodilators they received (in order to assess for an increased need for these medications). If the DSMC identifies any trend ($P<0.1$) towards more seizures, reduced survival, an increased need for sodium bicarbonate or bronchodilators they will be allowed to unblind themselves. If the trend is for increased short term need for sodium bicarbonate or bronchodilators, decreased survival or increased seizures in the topiramate group they will be allowed to stop the trial if they wish. However, if the trend favors topiramate over placebo, the DSMC will be expected to allow the trial to continue.

Below are the list and qualifications of DSMC Members: [name] (Neonatology Attending), [name] (Neonatal Nurse Practitioner), and [name] (Clinical Pharmacist).

PROTOCOL TITLE: Topiramate for infants receiving whole body cooling in neonatal encephalopathy

This protocol has risk category 2; namely “research involving greater than minimal risk, but presenting the prospect of direct benefit to the individual subjects.” As such we have developed an adverse event grading scale that is detailed below:

1. Adverse Event (AE) Grading and Attribution Scale

If adverse events should occur, they will be assessed using the following grading scale:

- 0= No adverse event or within normal limits
- 1= Mild adverse event
- 2= Moderate adverse event
- 3= Severe and undesirable adverse event
- 4= Life-threatening or disabling adverse event
- 5= Death caused by adverse event

Should adverse events occur, the following Attribution scale will be used to determine the relationship of the adverse event to the study.

- *Unrelated* - AE is clearly not related to the study procedure /intervention/- agent

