One concern on the use of topiramate is the potential to produce metabolic acidosis. From the data of Filippi (2010), although there were no significant effects of topiramate on metabolic acidosis, there was the suggestion in a post-hoc sub-group analysis that topiramate might increase metabolic acidosis in infants receiving deep hypothermia (cooled to 30-33 degrees Celsius) but not in those with moderate hypothermia. As we will be using moderate (not deep hypothermia) we do not foresee this as a problem. However, all infants undergoing cooling will have monitoring of their blood gases, and the detection of acidosis (especially metabolic acidosis) is common and easily treatable-sodium bicarbonate. Should this become a problem, we will therefore, be able to identify it early and respond to it promptly.

For severe adverse events, the drug will be discontinued and clinical intervention will be carried out. Any serious adverse events will be reported to the IRB immediately.

We will prospectively collect data on the number of doses of sodium bicarbonate each baby receives whilst receiving topiramate (or placebo), and the total number of doses of sodium bicarbonate received during their entire hospitalization. We will do the same for the number of doses of bronchodilators (for bronchospasm) the subjects receive. This information will be provided to the DSMC every 6 months for their review.

Potential side effects relevant to the population of this study are also described in lay terms in the informed consent form.

We have enough theoretical and experimental evidence to believe that the benefit of using topiramate in this group of patient outweighs the risk.

PROTOCOL TITLE: Topiramate for infants receiving whole body cooling in neonatal encephalopathy

Increased risk of brain injury can be detected by measuring the level of S-100 and UCHL1 in the urine/blood respectively in both groups of infants. Neurological examination at 18 month will identify infants in need of further follow up and/or intervention.

Therefore the risk-benefit ratio of this study is reasonable.

14) Potential Benefits to Subjects

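### Acidosis is compared between arms only through bicarbonate dose counts: blood gases already taken are not compared by agent, and the count behind the P<0.1 trigger is not named

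*Combined protocol and SAP*

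**What the plan says.** Section 13 (Risks to Subjects) states: "One concern on the use of topiramate is the potential to produce metabolic acidosis". It describes acidosis in cooled infants as common and treatable with bicarbonate. It then commits to two counts. The first is on study drug: "We will prospectively collect data on the number of doses of sodium bicarbonate each baby receives whilst receiving topiramate (or placebo". The second is the total over the whole hospital stay. Both go to the DSMC every six months.

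Section 11 (Provisions to Monitor the Data) lists what the DSMC receives for each infant, labelled drug A or B: seizures, survival to discharge, and "the number of doses of sodium bicarbonate and bronchodilators they received (in order to assess for an increased need for these medications". The trigger for unblinding covers the same items: "If the DSMC identifies any trend ($P<0.1$) towards more seizures, reduced survival, an increased need for sodium bicarbonate or bronchodilators". The test, its sidedness and the counting window are not given. Section 11 also says, of each newborn's safety, that "we will track the following variables closely during the intervention: blood gases" and several other variables.

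Section 8 (Procedures Involved) sets the gas schedule for every cooled infant: "Blood gases, blood glucose and ionized calcium levels are measured at the initiation of cooling and then every 6h until rewarming is complete". It says that enrolment does not change this frequency, and that the only added laboratory tests are UCHL1, S100β and topiramate troughs. The same section continues dosing past rewarming.

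Section 4 makes early acidosis one route to eligibility. Two of the four alternative signs of birth depression are "Blood pH < 7.0 within the first 1-hour of life" and "Base excess lower than -12 (i.e. base deficit more than 12) within the first hour of life".

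The Statistical Methods in Section 9 contain no comparison of pH, base deficit or any blood gas.

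**The concern.** The plan names a pharmacological harm, measures it directly many times in each infant, and then compares the arms on something else. A bicarbonate dose is a clinician's response to acidosis. Infants treated for the birth insult add doses in both arms, and acidosis that nobody treats adds none. A real drug effect on base deficit could therefore pass the DSMC unseen, or a chance difference in entry acidosis could look like a drug effect.

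Two gaps in specification add to this. The DSMC is not told which of two bicarbonate counts to test. And the scheduled gases stop before the last dose, so the final part of exposure has no scheduled acidosis measurement, although Section 11 says gases are tracked during the intervention.

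**Working it through.** **1. The plan's own figure.** No figure is given for any safety comparison. The only computed figure is the total of 42 for the seizure outcome (Section 9), which sets 21 per arm. With rates of 64% and 64%/3 = 21.3%, two-sided 0.05, 80% power and no continuity correction:

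n = [1.960·√(2 × 0.4267 × 0.5733) + 0.842·√(0.64 × 0.36 + 0.2133 × 0.7867)]² / 0.4267² = (1.371 + 0.531)² / 0.1820 = 19.9

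That is 20 per arm, or 40 in total, close to 42. The point below does not depend on it.

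**2. What is compared.**

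| Measure | Collected | In the by-agent DSMC list | In the P<0.1 trigger | In Statistical Methods |
|---|---|---|---|---|
| Bicarbonate doses on study drug | yes (Section 13) | doses listed, window not stated | need listed, window not stated | no |
| Bicarbonate doses, whole stay | yes (Section 13) | doses listed, window not stated | need listed, window not stated | no |
| pH, base deficit | every 6 h (Section 8) | no | no | no |

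**3. Gas window against dosing window.** Cooling lasts 72 h and rewarming 12 h, so scheduled gases end at 72 + 12 = 84 h. That gives 84/6 + 1 = 15 gases per infant and 15 × 42 = 630 in all. Both are ceilings: some gases precede the first dose, some infants may die, and Section 8 lets some laboratory tests stop once normal. Dosing is daily for five doses, and consent is sought after cooling has started. I take 24-h intervals, which fits the troughs drawn 24 h after doses 1, 3 and 5. With the first dose d hours after cooling starts (d is assumed), dose 5 falls at d + 96 h and its trough at d + 120 h:

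| d (h) | Dose 5 (h) | Last gas to dose 5 (h) | Last gas to trough (h) |
|---|---|---|---|
| 0 | 96 | 12 | 36 |
| 6 | 102 | 18 | 42 |
| 12 | 108 | 24 | 48 |
| 24 | 120 | 36 | 60 |

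If d exceeds 12 h, dose 4 (at d + 72 h) also falls after the last scheduled gas.

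**4. Dilution (illustration).** The documents give no rate of bicarbonate use, so every rate here is assumed. Take any bicarbonate use as yes/no, 21 per arm, two-sided P<0.1. A share s of infants in both arms receive it for the birth insult, 10% of the rest receive it for other reasons, and the drug creates a need in a fraction q of those still untreated. Then control rate = 1 − (1 − s) × 0.9 and topiramate rate = 1 − (1 − s) × 0.9 × (1 − q). With difference Δ and mean rate p̄:

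Power = Φ{[Δ√21 − 1.645√(2p̄(1 − p̄))] / √(sum of the two binomial variances)}

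For s = 0.4 and q = 0.3 the rates are 0.46 and 0.622, and power = Φ[(0.742 − 1.159)/0.695] = Φ(−0.60) = 27%.

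| s | Power, q = 0.2 | Power, q = 0.3 |
|---|---|---|
| 0 | 44% | 67% |
| 0.2 | 25% | 42% |
| 0.4 | 17% | 27% |
| 0.6 | 13% | 19% |

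These are values at full enrolment; earlier six-monthly looks have fewer infants. A dose count can still register extra doses in infants already treated, so yes/no use overstates the loss. Only bicarbonate given after the first dose dilutes the on-study-drug count.

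**5. Chance imbalance.** With an assumed 30% to 70% of infants acidotic at entry, a difference between arms of 20 points or more (5 or more infants of 21) arises by chance in about 13% to 16% of trials.

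**6. What the gases could show (illustration).** Assume equal correlation ρ between gases in one infant, and the mean of 14 later values adjusted for the first. The difference detectable with 80% power at two-sided 0.05, in SDs of a single value, is 2.802 × √(2/21) × √v = 0.865 × √v, with v = (1 + 13ρ)/14 − ρ². For ρ = 0.3, 0.5 and 0.7 this gives 0.44, 0.46 and 0.42 SD, against 0.86 SD for one unadjusted value. If the first dose comes at 12 h and 12 later values remain, ρ = 0.5 gives v = (1 + 11 × 0.5)/12 − 0.25 = 0.292 and 0.865 × 0.540 = 0.47 SD, so little is lost.

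**The case against.** The strongest case against runs as follows.

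- **The count answers its own question.** It is meant to show need for medication, and it does.
- **The on-study-drug count already excludes bicarbonate given before the first dose.** Section 11's stopping clause speaks of short-term need, which fits that count.
- **Entry acidosis is not universal.** It is reached through two of four alternative criteria, and its rate is not given. The trial is randomised and blinded.
- **The DSMC sees more than the counts.** It reviews safety data every six months, its chair receives all adverse event reports, and survival is shown beside the counts with its own trigger.
- **Later gases may be taken for clinical reasons.** Section 8 describes a standard-care schedule and does not exclude them.
- **The protocol does not expect a problem.** Section 13 reports no significant effect in the cited safety study, and only a post-hoc suggestion in deeply cooled infants.
- **Base deficit is not a clean measure either.** It is altered by the bicarbonate given to treat it, and a worst value depends on how many gases are taken.

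Most of this stands, and it limits the point. It does not supply a between-arm comparison of pH or base deficit, since no acidosis threshold or by-arm acidosis analysis is stated for the adverse event route. Nor does it say which count is tested. The last item is a reason to keep to scheduled times and to read gases and counts together.

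**Conclusion.** The point holds as a low-cost improvement to safety monitoring; the primary efficacy analysis is unaffected. A harm named by the protocol has one prespecified between-arm measure, a treatment-decision count whose window is unstated, while up to 15 direct measurements per infant go uncompared. Scheduled gases end at least 12 h before dose 5 and at least 36 h before its trough, given 24-h intervals. The power, imbalance and detectable-difference figures show direction under assumed rates and correlations; they are not estimates for this trial.

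A reader might infer more than the documents support:

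- **That entry acidosis biases the comparison.** Under blinded randomisation it adds noise and chance imbalance.
- **That the DSMC has no access to acidosis information.** Adverse event reports reach its chair; what is missing is a prespecified comparison of gases.
- **That bicarbonate given before study drug necessarily contaminates the measure.** The on-study-drug count excludes it.
- **That 630 usable gases are being ignored.** That is a full-schedule ceiling which includes pre-dose values.
- **That no gas can be taken after rewarming.** None is scheduled, but none is excluded. The two sections differ in the window they describe, and this is a gap in specification more than a flat contradiction.

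**What to change.** 1. Add to the six-monthly DSMC report, by agent A/B, base deficit and pH after the first dose, each adjusted for the last pre-dose value. Use scheduled times only, summarised as the mean or the worst scheduled value, so that infants sampled more often do not look worse for that reason. Present these as supporting data beside the dose counts, without a new automatic trigger.
2. State in Section 11 that the existing bicarbonate trigger uses the on-study-drug count. Keep the whole-hospitalisation total as a secondary figure, read alongside survival because early death shortens it.
3. Reconcile Sections 8 and 11 on the period over which blood gases are tracked, against the dosing period. The sponsor must settle which window is intended.

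The cost is a few report columns and some protocol wording. Items 1 and 2 need no new samples, but gases already scheduled cannot describe the period after rewarming. The DSMC has one more variable to interpret. Because bicarbonate treatment itself changes base deficit, gases and dose counts should be read together.
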